10.3.2.1 Management of Adverse Events

With the exception of presumed cardiac or intestinal ischemia, the initial management of AEs may include dose reduction or temporary interruption of study drug dosing. After dose interruption, study drug may be restarted at a reduced dose of 0.5 mg or 1 mg every 6 to 12 hours. At the discretion of the investigator, the dose may then be increased to the previous dose level. Careful assessment of concomitant medications and treatment (particularly albumin dosing) and their potential relationship to the AE should be undertaken and adjusted as per standard of care and investigator discretion. If possible, study drug dosing should be restarted promptly and/or maintained at usual or reduced dosing particularly for the first 4 days of study drug administration. Investigators are encouraged to discuss any dosing questions with the Medical [contact] Management of Fluid Overload

Volume overload in this context refers to intravascular volume overload manifested as pulmonary congestion or overt pulmonary edema. Subjects with increasing dyspnea, cough, orthopnea, or tachypnea should be carefully evaluated for evidence of pulmonary edema (physical examination and, as judged by the investigator to be indicated, chest X-ray or other investigations). In subjects with fluid overload, especially those with respiratory events

(dyspnea, respiratory distress), careful assessment of concomitant albumin and temporary albumin dose reduction or discontinuance may be the most appropriate initial management. Judicious, short term use of temporary diuretic therapy as per standard of care may be undertaken at the discretion of the investigator in some subjects in whom a response to diuretic therapy is expected. If fluid overload requiring intervention persists after these initial measures, further management should include dose reduction or temporary interruption of study drug dosing as above.

10.4 Treatment Discontinuation

- Treatment should be continued until 24 hours after 2 consecutive SCr values no more than 1.5 mg/dL have been obtained, OR up to a maximum of 14 days (maximum of 15 days if SCr first reaches 1.5 mg/dL on Day 14).
- If on Day 4 (after a minimum of 10 doses) SCr is at or above baseline value, study drug should be discontinued.
- Treatment must be discontinued when the subject is to undergo RRT, liver transplantation, TIPS or vasopressor therapy.
- Dosing must be permanently discontinued if an event of cardiac ischemia or mesenteric ischemia occurs.

10.5 Assessment of Recurrence

Any subject with a SCr value of at least 2.25 mg/dL after achieving verified HRS reversal, but prior to transplant/discharge/Day 14, will be assessed for HRS Type 1 recurrence. HRS recurrence by Day 30 is defined as another episode of HRS Type 1, by Day 30, after achieving verified HRS reversal, characterized by rapidly progressive worsening in renal function to a SCr at least 2.25 mg/dL, without sustained improvement in renal function (less than 20% decrease in SCr and SCr at least 2.25 mg/dL) at least 48 hours after diuretic withdrawal and the beginning of plasma volume expansion with albumin, and meeting all applicable inclusion and exclusion criteria (as outlined in Section 8.3 and Section 8.4) defining the initial diagnosis of HRS Type 1.

Specifically, these criteria are as follows:

- 1. The subject had rapidly progressive worsening in renal function to a SCr at least 2.25 mg/dL and met a trajectory for SCr to double over 2 weeks.
- 2. The subject had no sustained improvement in renal function (less than 20% decrease in SCr and SCr at least 2.25 mg/dL) at least 48 hours after diuretic withdrawal and the beginning of plasma volume expansion with albumin.
- 3. The subject had no sepsis or uncontrolled bacterial infection.
- 4. If there is documented or suspected infection, the subject has at least 2 days of anti-infective therapy.
- 5. The subject does not have shock.
- 6. The subject does not have current or recent (within 4 weeks) treatment with or exposure to nephrotoxic agents: eg, aminoglycosides, amphotericin, cyclosporine A, cisplatin, nonsteroidal anti-inflammatory drugs (NSAIDs: eg, ibuprofen, naproxen, diclofenac), significant exposure to radiographic contrast agents (large doses or multiple injections of iodinated contrast media, eg, during coronary or abdominal angiogram.

Note: Up to 3 doses of an NSAID within the prior month is acceptable.

Note: Use of short-term (less than 2 weeks) oral neomycin for acute encephalopathy is acceptable.

- 7. The subject had no superimposed acute liver injury or exposure to nephrotoxic agents.
- 8. Proteinuria was less than 500 mg/day.
- 9. The subject does not have evidence of obstructive uropathy or parenchymal renal disease on ultrasound or other imaging.
- 10. The subject does not have tubular epithelial casts, heme granular casts, hematuria or microhematuria (greater than 50 red blood cells per high power field in the absence of recent catheterization) on urinalysis.

Note: Urine sediment examination is required to exclude presence of heme granular casts and other clinically significant casts.

The investigator will determine whether the subject has had a recurrence of HRS Type 1. If the investigator cannot exclude a recurrence of HRS Type 1, then the subject will be considered to have HRS Type 1 recurrence. HRS Type 1 recurrence will be monitored as follows: Recurrence of HRS Type 1 during the follow-up period (after discharge or Day 14) will be assessed based upon the investigator's opinion and serious AE data collected up to 30 days after end of treatment. Following the initial hospital discharge, all re-hospitalizations within 30 days after end of treatment (except for planned hospital admissions or procedures as described in the protocol) are to be recorded as an SAE. Re-hospitalizations will require an investigator assessment and opinion regarding possible recurrence of HRS Type 1. All available relevant medical records, MedWatch forms, discharge summaries or other relevant source documents should be requested and reviewed for all SAEs, including all hospitalizations, until 30 days after discontinuation of study drug.

HRS Type 1 recurrence beyond 30 days after end of treatment will be further monitored based on requests for retreatment as outlined in Section 10.6 of the protocol.

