8.4 Exclusion Criteria

If any of the following exclusion criteria are met, the subject will **not** be enrolled:

- 1. Serum creatinine level greater than 7.0 mg/dL.
- 2. At least 1 event of LVP at least 4 L within 2 days of randomization.

Note: The investigator must review any paracentesis performed in the pre-enrollment period and volume status after paracentesis must be considered carefully; as per standard of care, adequate replacement of fluid removed with albumin is required.

3. Sepsis and/or uncontrolled bacterial infection (eg, persisting bacteremia, persisting ascitic fluid leucocytosis, fever, increasing leucocytosis with vasomotor instability).

Note: Sepsis is defined as documented active, untreated infection and presence of SIRS. SIRS is defined as the presence of 2 or more of the following findings: temperature greater than 38°C or less than 36°C; heart rate greater than 90/min; respiratory rate greater than 20/min or partial pressure of arterial carbon dioxide (PaCO₂) less than 32 mm Hg; white blood cell (WBC) count greater than 12,000 cells/μL or less than 4,000/ μL).

Note: Patients with decompensated liver disease frequently have SIRS criteria in the absence of uncontrolled infection or sepsis. Subjects with SIRS criteria, in the absence of active, untreated infection, and reasonably attributed to decompensated liver disease or alternate causes (eg, hepatic hydrothorax, acute alcoholic hepatitis) should be enrolled after discussion with the sponsor via the Medical Hotline, assuming they meet all subject selection criteria.

- 4. Less than 2 days anti-infective therapy for documented or suspected infection.
- 5. Shock.

Note: Shock is defined as hypotension (MAP less than 70 mm Hg or a decrease greater than 40 mm Hg in systolic blood pressure from baseline) with evidence of hypoperfusion abnormalities (eg, peripheral cyanosis, hypothermia, marked asthenia, pallor, obtundation not attributable to hepatic encephalopathy).

6. Current or recent (within 4 weeks) treatment with or exposure to nephrotoxic agents: eg, aminoglycosides, amphotericin, cyclosporine A, cisplatin, nonsteroidal anti-inflammatory drugs (NSAIDs: eg, ibuprofen, naproxen, diclofenac), significant exposure to radiographic contrast agents (large doses or multiple injections of iodinated contrast media, eg, during coronary or abdominal angiogram.

Note: Up to 3 doses of an NSAID within the prior month is acceptable.

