Note: Use of short-term (less than 2 weeks) oral neomycin for acute encephalopathy is acceptable.

- 7. Estimated life expectancy of less than 3 days.
- 8. Superimposed acute liver injury due to drugs (eg, acetaminophen), dietary supplements, herbal preparations, viral hepatitis, or toxins (eg, *Amanita* toxin with mushroom poisoning, carbon tetrachloride), with the exception of acute alcoholic hepatitis.

Note: subjects meeting criteria for drug, dietary supplement or herbal preparation induced liver injury (http://livertox.nih.gov/; Chalasani et al, 2014) should be excluded

- 9. Proteinuria greater than 500 mg/day.
- 10. Evidence of obstructive uropathy or parenchymal renal disease on ultrasound or other imaging.
- 11. Tubular epithelial casts, heme granular casts, hematuria or microhematuria (greater than 50 red blood cells per high power field in the absence of recent catheterization) on urinalysis.

Note: Urine sediment examination is required to exclude presence of heme granular casts and other clinically significant casts.

- 12. Subjects known to be pregnant; all women of child-bearing age and potential must have a negative pregnancy test.
- 13. Severe cardiovascular disease, including, but not limited to, unstable angina, pulmonary edema, congestive heart failure requiring increasing doses of drug therapy, or persisting symptomatic peripheral vascular disease, myocardial infarction or stable chronic angina within the past 12 months, or any other cardiovascular disease judged by the investigator to be severe.
- 14. Current or recent (within 4 weeks) RRT.

- 15. Participation in other clinical research involving investigational medicinal products within 30 days of randomization.
- 16. TIPS within 30 days of randomization.
- 17. Use of vasopressors (eg, norepinephrine, epinephrine or vasopressin, dopamine or other vasopressors) of at least 3 consecutive days within prior 14-day screening period. Patients receiving a vasopressor other than midodrine within 24 hours of qualifying SCr are excluded, ie, a 24-h washout is required prior to enrollment.
 - *Note*: Patients receiving midodrine and octreotide may be enrolled. Midodrine and octreotide treatment must be stopped prior to randomization.
- 18. Known allergy or sensitivity to terlipressin or another component of the study treatment.

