10.6 Retreatment

If judged by the investigator to be potentially beneficial, subjects who demonstrate at least a partial response during the initial treatment course (at least 30% reduction in SCr) who develop recurrence of HRS Type 1 during the study or follow-up period may be retreated with initially assigned blinded study drug for a maximum of 14 days (from the beginning of the retreatment, treatment and study procedures will be identical to the initial therapy). To qualify for retreatment, the subject must again meet the study inclusion/exclusion criteria (Section 8.3 and Section 8.4) and the sponsor must be contacted prior to initiation of retreatment. Retreatment may occur within 90 days of the subject's first dose of study drug. Subjects will not be re-randomized or re-stratified for the retreatment cycle. Retreated subjects should follow the same schedule of assessment as performed in the original treatment period. The follow-up schedule will be based upon the original randomization. AEs for retreated subjects will be followed for 7 days postdose or discharge, whichever comes first.

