• Incidence of HRS reversal in the SIRS subgroup, defined as the percentage of SIRS subjects with HRS reversal. HRS reversal is defined as the percentage of subjects with a SCr value not more than 1.5 mg/dL while on treatment by Day 14 or discharge (SCr values after RRT, TIPS, liver transplant, or open-label vasopressor use will be excluded). This endpoint will be summarized by treatment group and analyzed similarly to HRS reversal. The SIRS subgroup is defined as any subject with at least 2 of the following criteria: WBC less than 4,000 or greater than 12,000 cells/μL; HR greater than 90 bpm; temperature greater than 38°C or less than 36°C; respiratory rate of greater than 20/min; HCO₃ less than 21 mmol/L; the latter criterion represents an approximation of the SIRS criterion PaCO₂ of less than 32 mm Hg, derived from the observed HCO₃ in subjects with HRS in whom a PaCO₂ value was available (from the TAHRS study) and the calculated HCO₃ in subjects with decompensated liver disease and PaCO₂ of less than 32 mm Hg.

Incidence of verified HRS reversal without HRS recurrence by Day 30. HRS Type 1 recurrence is defined in Section 10.5. Incidence of verified HRS reversal, defined as the percentage of subjects with 2 consecutive SCr values no more than 1.5 mg/dL at least 2 hours apart, while on treatment up to 24 hours after the final dose of study drug, by Day 14 or discharge. Subjects must be alive without RRT for at least 10 days after achieving verified HRS reversal. SCr values after RRT, transjugular intrahepatic portosystemic shunt (TIPS), liver transplant, or open-label vasopressor use will be excluded from primary end point analysis. SCr values obtained after midodrine administration will be included if midodrine was started on Day 1, was administered for no more than 24 hours, and the subject was enrolled on or after 17 August 2018. SCr values will also be included if obtained after the administration of a single dose of dobutamine. This endpoint will be summarized by treatment group and analyzed similarly to HRS reversal.

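### Item 7 of the recurrence definition (Section 10.5) omits the alcoholic hepatitis exception of exclusion 8 and contradicts item 6 on nephrotoxins, so some relapses could count as successes in the fourth secondary endpoint

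*Combined protocol and SAP*

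**What the plan says.** Section 15.3.6.2 lists the endpoint as "Incidence of verified HRS reversal without HRS recurrence by Day 30. HRS Type 1 recurrence is defined in Section 10.5". It is one of four secondary endpoints tested by the Hochberg procedure.

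Section 10.5 requires a recurrence to meet the applicable entry criteria of Sections 8.3 and 8.4, and then sets those criteria out in a numbered list of ten items. Two items matter here:

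- Item 6: "The subject does not have current or recent (within 4 weeks) treatment with or exposure to nephrotoxic agents". Its notes add "Up to 3 doses of an NSAID within the prior month is acceptable" and the same neomycin allowance as Section 8.4.
- Item 7: "The subject had no superimposed acute liver injury or exposure to nephrotoxic agents".

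At entry, exclusion 8 in Section 8.4 bars superimposed acute liver injury from drugs, supplements, herbal preparations, viral hepatitis or toxins, "with the exception of acute alcoholic hepatitis". The note to exclusion 3 expects such subjects. Of those who meet SIRS criteria without active untreated infection, for reasons including alternate causes, it says: "eg, hepatic hydrothorax, acute alcoholic hepatitis) should be enrolled after discussion with the sponsor via the Medical Hotline", provided all selection criteria are met.

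Section 10.5 also has the investigator decide whether recurrence occurred, and counts a case as recurrence if it cannot be excluded. For retreatment, Section 10.6 says "the subject must again meet the study inclusion/exclusion criteria (Section 8.3 and Section 8.4").

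**The concern.** The ten items are joint conditions: an episode is a recurrence only if all are met. An item stricter than its entry counterpart therefore removes episodes from the recurrence count. A subject who reversed and whose relapse is not counted remains a success in this endpoint.

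Item 7 is stricter than entry on acute liver injury and stricter than item 6 on nephrotoxins. Read literally, it can only move relapses into the success column. Only subjects with verified reversal can be affected, so if relapse rates and affected shares are similar in the two arms, the arm with more reversals gains more in absolute terms. At stake is a bias in a tested secondary claim about durability. Sites may also resolve the conflict differently.

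**Working it through.** **Step 1. The passages side by side.**

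| Subject matter | Entry (8.4) | Recurrence (10.5) | Match? |
|---|---|---|---|
| Nephrotoxins, 4-week window | Exclusion 6 | Item 6 | Yes |
| NSAID allowance, up to 3 doses | Note to exclusion 6 | Note to item 6 | Yes |
| Short-term oral neomycin | Note to exclusion 6 | Note to item 6 | Yes |
| Acute liver injury, listed causes | Exclusion 8 | Item 7, no causes listed | No |
| Acute alcoholic hepatitis exempt | Exclusion 8 | Item 7, no exemption | No |
| Nephrotoxins, no window or allowance | None | Item 7, second clause | Contradicts item 6 |

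A subject with two NSAID doses in the prior month passes item 6 and fails item 7.

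**Step 2. A hypothetical subject.** Suppose a subject with acute alcoholic hepatitis at entry has verified reversal on Day 5, with SCr of at most 1.5 mg/dL, and reaches 2.6 mg/dL on Day 12. The rise is at least 2.6 / 1.5 = 1.73-fold over 7 days; Table 21–1 requires 1.62. Assume the other items are met, including no sustained improvement at least 48 hours after diuretic withdrawal and the start of albumin, and that the hepatitis is still present. Under exclusion 8 the hepatitis is no obstacle. Under item 7 read literally, the episode is not a recurrence.

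**Step 3. Size.** The plan states no figure to reproduce, and gives neither a recurrence rate nor the share of subjects affected. Assume, equally in both arms:

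- relapse by Day 30 among reversers: r = 10% to 30%;
- share of those relapses that fail item 7 only: s = 10% to 40%;
- item 7 always applied literally.

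Hidden relapses as a fraction of reversers = r × s, from 0.10 × 0.10 = 0.01 to 0.30 × 0.40 = 0.12.

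*With the rates in Table 15–2, Scenario 1 (34% and 12%, an interim success scenario):*

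- terlipressin: 34 × 0.01 = 0.34 to 34 × 0.12 = 4.1 points;
- placebo: 12 × 0.01 = 0.12 to 12 × 0.12 = 1.4 points;
- overstated difference: 22 × 0.01 = 0.2 to 22 × 0.12 = 2.6 points.

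*With rates closer to the planning basis.* The planned terlipressin rate is not visible in the public copy. Taking placebo at 12.5%, 200 and 100 subjects, boundaries 2.79651 and 1.97743 and a pooled two-stage Z, the stated 89.76% power implies about 29.4%.

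- terlipressin: 200 × 0.294 × (0.01 to 0.12) = 0.6 to 7.1 subjects;
- placebo: 100 × 0.125 × (0.01 to 0.12) = 0.1 to 1.5 subjects;
- overstated difference: (29.4 − 12.5) × (0.01 to 0.12) = 0.2 to 2.0 points.

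**Step 4. Effect on the test.** On the planning basis, the pooled unstratified Z evaluated at these rates is:

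- r = 10%, s = 10%: 3.05 with the literal list, 3.03 with aligned wording (shift 0.02);
- r = 30%, s = 40%: 2.85 with the literal list, 2.59 with aligned wording (shift 0.26).

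At the extreme, the aligned two-sided p is 2 × (1 − Φ(2.59)) = 0.0096, still below the smallest comparator in Table 15–4, 0.011998. In this illustration the conclusion does not change; it could in a closer result. The plan's own test is a stratified CMH, so these Z values are approximate.

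**The case against.** The strongest reply is that item 7 is shorthand. The lead-in ties the list to Sections 8.3 and 8.4, where the exception stands, and a loose second clause should not cancel the explicit notes directly above it. After discharge or Day 14, recurrence rests on investigator opinion and serious adverse event data, so the list is not applied mechanically. An investigator who sees item 7 conflict with Section 8.4 has reason for doubt, and doubt defaults to recurrence. The Amendment 2 summary also mentions sensitivity analyses on that default in Section 15.3.6.3, but that section is not visible in the public copy, so what they cover cannot be judged.

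Much of this stands: miscounting is possible, not certain. It does not settle the matter. The list is presented as the specific statement of the criteria, and the Amendment 2 summary says the revision was meant to spell out every parameter, so a site may fairly apply it as written. The default covers doubt, and item 7 read literally gives a definite ground for ruling recurrence out.

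Three stronger readings are tempting but not supported:

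- **That Section 10.5 drops the nephrotoxin allowances.** It does not. Item 6 repeats both, including "Use of short-term (less than 2 weeks) oral neomycin for acute encephalopathy is acceptable". The fault is that item 7 contradicts item 6.
- **That a subject would be retreated for recurrence and still counted recurrence-free.** This needs recurrence to be read one way in Section 10.6 and another in Section 10.5, and no passage provides for two determinations. The sections are not fully aligned, since 10.6 admits subjects after a partial response while 10.5 presupposes verified reversal, but the documents do not establish that outcome.
- **That failing a listed item always overrides the default to recurrence.** No passage says so.

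**Conclusion.** Wrong as written: an internal inconsistency in the definition behind one secondary endpoint. The textual conflict is certain. How many relapses would be miscounted is not known, because the documents give neither the share with alcoholic hepatitis or a permitted exposure nor the relapse rate.

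The range of about 0.2 to 2.6 points in the arm difference (0.2 to 2.0 on the back-solved planning rates) is illustrative. It assumes equal relapse rates and shares in both arms and literal use of item 7 throughout, so for given r and s it leans high. Literal use moves relapses only towards success. That the better arm gains more depends on the equal-share assumption. A reader might infer a threat to the trial's main result; there is none, because the primary endpoint does not use the recurrence definition, and power and alpha are untouched.

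**What to change.** Before unblinding, reconcile item 7 of Section 10.5 with exclusion 8 of Section 8.4 and with item 6, so that the endpoint definition of recurrence uses the same criteria as entry. One way is to cite exclusion 8 as it stands and delete the nephrotoxin clause from item 7, since item 6 already covers that ground.

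Add one sentence to Section 15.3.6.2 stating that a subject retreated under Section 10.6 for recurrence by Day 30, after verified reversal, is classed as having recurrence in this endpoint. This concerns classification only; who may be retreated is for the clinical team.

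The cost is a short wording amendment with no new data collection. The reported recurrence-free rate may become slightly less favourable.

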10.6 Retreatment

If judged by the investigator to be potentially beneficial, subjects who demonstrate at least a partial response during the initial treatment course (at least 30% reduction in SCr) who develop recurrence of HRS Type 1 during the study or follow-up period may be retreated with initially assigned blinded study drug for a maximum of 14 days (from the beginning of the retreatment, treatment and study procedures will be identical to the initial therapy). To qualify for retreatment, the subject must again meet the study inclusion/exclusion criteria (Section 8.3 and Section 8.4) and the sponsor must be contacted prior to initiation of retreatment. Retreatment may occur within 90 days of the subject's first dose of study drug. Subjects will not be re-randomized or re-stratified for the retreatment cycle. Retreated subjects should follow the same schedule of assessment as performed in the original treatment period. The follow-up schedule will be based upon the original randomization. AEs for retreated subjects will be followed for 7 days postdose or discharge, whichever comes first.

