14.2 Collection of Adverse Events/Serious or Unexpected

Any AE occurring prior to signing the ICF should be considered medical history or a pre-existing condition and will be collected on the Medical History eCRF.

All AEs will be assessed and recorded beginning with study drug administration until 7 days after discontinuation of study drug and at each evaluation. Adverse events considered serious will be assessed and recorded until 30 days after discontinuation of study drug, excluding deaths, which will be collected up to 90 days after the first dose of study drug.

The investigator will collect and record all necessary data including investigations that were performed for any AE of special interest, ie, an ischemic abdominal event, ischemic cardiac event, or bronchospasm-related respiratory event.

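### Section 10.6 stops adverse event follow-up of retreated subjects at discharge and leaves serious event and death collection for the second course unclear, in conflict with itself and with the general safety windows

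*Combined protocol and SAP*

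**What the plan says.** Section 10.6 (Retreatment) lets subjects with at least a partial response and a later recurrence be treated again. They "may be retreated with initially assigned blinded study drug for a maximum of 14 days", and "Retreatment may occur within 90 days of the subject's first dose of study drug". The Synopsis allows one such cycle.

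On follow-up, Section 10.6 makes four statements:

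- The AE window is given as follows: "AEs for retreated subjects will be followed for 7 days postdose or discharge, whichever comes first".
- Procedures in the second course are tied to the first: "from the beginning of the retreatment, treatment and study procedures will be identical to the initial therapy".
- The clock for later contacts is not restarted: "The follow-up schedule will be based upon the original randomization".
- The timetable of assessments used in the first course applies again.

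The general rules are in Sections 13.4.4, 14.2 and 15.1 and in Table 13-1. AEs are recorded until 7 days after study drug stops, and none of these places mentions discharge. For SAEs, Section 14.2 says "Adverse events considered serious will be assessed and recorded until 30 days after discontinuation of study drug". Deaths have their own limit in that section, "which will be collected up to 90 days after the first dose of study drug". Section 13.2.4 ends the follow-up period 90 days after the start of treatment. Section 14.1.6 defines SAEs as a subset of AEs. None of the general rules mentions retreatment.

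**The concern.** Confirming safety is a stated objective, and retreatment is a second exposure to a drug for which the protocol itself names ischemic and respiratory risks (Sections 5.3.3 and 13.4.4.1). The second course should be observed at least as closely as the first, yet Section 10.6 gives it a shorter AE window that closes at discharge. It also keeps follow-up on the original clock. A second course can fall late in the 90 days, so the time left for collecting deaths after it may be short or nil.

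Two sites could read the text differently. One could stop all event collection at discharge, and another could continue SAE collection for 30 days. Harms of repeat exposure would then be undercounted, or counted by different rules at different sites.

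**Working it through.** The plan gives no figure to reproduce on this point. The check sets the windows side by side and then counts days.

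**Step 1. Windows compared.**

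| Event | First course (13.4.4, 14.2, 15.1, Table 13-1) | Second course (10.6) |
|---|---|---|
| AEs | 7 days after last dose, no stop at discharge | 7 days or discharge, whichever is earlier |
| SAEs | 30 days after study drug stops | Not mentioned separately |
| Deaths | To 90 days after first dose | Not mentioned; follow-up stays on the original clock |

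The left column should also apply to the second course if its procedures and schedule match those of the first. The AE row shows that Section 10.6 does not keep to this.

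**Step 2. Non-serious AEs.** Days lost = 7 − (days from last dose to discharge), when discharge comes within 7 days. Discharge on the last dosing day loses 7 − 0 = 7 days. Discharge 3 days later loses 7 − 3 = 4.

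**Step 3. Deaths.** Inputs:

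- Day 1 is the first day of study drug (15.3.7).
- A full second course is 14 days (10.6).
- Death collection is taken to close on Day 90 (13.4.4, 14.2).

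For a course starting on Day S, the last dosing day is S + 13. The days of death collection left after it are 90 − (S + 13) = 77 − S.

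| Start day S | Last dosing day | Days of death collection left |
|---|---|---|
| 1 (first course) | 14 | 76 |
| 47 | 60 | 30 |
| 48 | 61 | 29 |
| 70 | 83 | 7 |
| 77 | 90 | 0 |
| 90 | 103 | −13 |

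For the Day 90 start, a 30-day SAE window would end on Day 103 + 30 = Day 133.

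**Step 4. Sensitivity to the reading.**

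- *Retreatment must be completed by Day 90.* Then S is at most 77, and full courses starting on Days 48 to 77 have 29 down to 0 days left. The shortfall against 30 days remains.
- *Retreatment must only start by Day 90.* Then courses starting on Days 78 to 90 have 1 to 13 dosing days after Day 90. If the latest start is counted as Day 91 while collection closes on Day 90, all 14 dosing days fall after it.
- *Both limits counted as Day 91.* The thresholds move from 47 and 77 to 48 and 78. The largest overrun stays at 104 − 91 = 13 days.
- *The 15-day exception carries over to retreatment.* The thresholds become 46 and 76.
- *Shorter courses.* For a course of k days, 30 days remain if S is at most 61 − k. With k = 7 that is Day 54, so the gap narrows but does not close.

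**The case against.** **SAEs.** A reader might infer that a subject discharged on the last retreatment day has no SAE follow-up where 30 days were due. The documents do not establish that. The 30-day rule has no exemption for retreatment. Section 13.4.4 itself states a 7-day rule for AEs followed by a separate 30-day rule for SAEs, and the sentence in 10.6 fits that pattern. Section 10.5 asks for review of records on all SAEs to 30 days after study drug stops, and Section 14.3.1 requires every SAE to be reported. Still, 10.6 makes no exception for SAEs, and they are AEs by definition. The total loss is therefore one possible reading, and the text does not exclude it.

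**Deaths.** A fatal event is an SAE under 14.1.6, so the 30-day rule might capture it. In the first course the separate rule for deaths lengthens collection, since 14 + 30 = Day 44 is well before Day 90. Table 13-1 also records mortality throughout the active and follow-up periods. But 13.4.4 and 14.2 take deaths out of the 30-day rule, 13.2.4 closes follow-up at 90 days, and 10.6 does not reset the clock. The Day 90 contact has a window of 14 days either side, so some contacts may come as late as Day 104. Others may come as early as Day 76, and the stated limit remains 90 days.

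**Latest start.** A reader might take it as settled that retreatment can begin on Day 90. The text does not say whether the 90 days limit the start or the completion.

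**Which arm loses events.** A reader might infer that missed events fall mainly on terlipressin. Using reversal rates from the two earlier placebo-controlled trials as a stand-in for eligibility, with 2:1 allocation, the terlipressin share would be (2 × 34)/(2 × 34 + 13) = 84% or (2 × 24)/(2 × 24 + 15) = 76%. This is only an illustration: reversal is not the eligibility rule, and retreatment also requires recurrence, for which no rate by arm is given.

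**Conclusion.** The concern holds as a conflict in the text with a limited, definite loss. Section 10.6 contradicts its own statement that the second course follows the first, and it contradicts 13.4.4, 14.2, 15.1 and Table 13-1.

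- **Non-serious AEs.** Where the 10.6 sentence is applied, events after an early discharge go unrecorded, up to all 7 days of the window.
- **SAEs.** Whether the 30-day window covers the second course is undefined.
- **Deaths.** On the stated 90-day limit, a full 14-day second course starting after Day 47 has fewer than 30 days of post-treatment collection. Collection ends before the last dose only for starts after Day 77, and only if the 90-day limit applies to the start.

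The death figures assume a full 14-day course and collection closing on Day 90. The number of retreated subjects is not given, so the number of events that could be lost cannot be estimated. Efficacy conclusions are not touched, because Section 15.3.6 uses the initial course and evaluates retreatment separately. The plan should be corrected, but this does not threaten the primary result.

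**What to change.** 1. In Section 10.6, delete the stop at discharge. State that the Section 14.2 windows, 7 days for AEs and 30 days for SAEs, run from the last retreatment dose whether or not the subject has been discharged.
2. For retreated subjects, collect deaths to the later of Day 90 or the end of that 30-day window. This is a new rule; the SAE and AE windows in item 1 are the plan's own.
3. Reconcile 10.6, 13.2.4, 13.4.4, 14.2, 15.1 and Table 13-1. State whether the 90-day limit on retreatment refers to its start or its completion; that choice is the sponsor's.
4. Add a line to 15.3.6.4 on how second-course events are reported, since separate evaluation is stated only under the efficacy analyses.

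The cost is an amended paragraph with matching edits, and a few extra follow-up contacts for retreated subjects. No treatment rule has to change.
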